6.7.1.1. IMGC936 Dosage

The calculated dose of IMGC936 will be administered based on the participant's body weight at Cycle 1, Day 1. Body weight will be measured at screening and Day 1 of each cycle. Significant ($\geq 10\%$) change in body weight from baseline should prompt recalculation of dose. Refer to the pharmacy manual for further instructions on allowable parameters for dose rounding.

IMGC936 should not be administered as an IV push or bolus. All doses of IMGC936 will be diluted in D5W and administered as an IV infusion with a commercially available infusion pump. All infusion pumps must be calibrated in accordance with the institutional standards, policies, and procedures to ensure consistent, accurate delivery of IMGC936.

Infusion or allergic reactions may occur with the infusion of mAb and other protein-based therapeutics. Precautions for anaphylaxis should be observed during administration. Refer to Section 7.1 for specific guidelines regarding the management of infusion reactions. Supportive care measures consistent with optimal care will be provided throughout the study according to institutional standards.

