14.4. Study Drug Exposures and Concomitant Medications

Study drug exposures and concomitant medications will be summarized by descriptive statistics. The summary of study drug exposure will include descriptive statistics as well as frequency counts for the number of doses or cycles received, the total dose administered as well as the total

dose intended, and the dose intensity, which is calculated as percentage of total dose actually administered divided by total dose intended during the whole treatment period.

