# 7.1. Exposure

Study treatment attributes to be used in analyses will include the following. Summary tables will be provided for each dose level of IMGC936.

- Number of treatment doses (or cycles) is defined as the number of infusions of IMGC936.
- Treatment duration (weeks) = [(last infusion date first infusion date) + length of cycle] / 7
- Total cumulative dose (mg) = sum of actual dose administered in all cycles while the patient is on study drug
- Actual dose intensity (mg/kg/dose) = total cumulative dose (mg) / baseline weight (kg)/(total treatment duration (weeks) / number of weeks in each cycle)
- Relative dose intensity (%) = actual dose intensity/planned dose intensity\*100%

A listing will be provided with the information from all study drug administration eCRFs over the treatment period.

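### SAP 7.1 divides mg given by baseline weight, so actual dose intensity is wrong once a dose has been recalculated for a weight change of 10% or more

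*SAP*

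**What the plan says.** SAP 7.1 (Exposure) sets out three linked quantities:

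- The numerator is in mg actually given: "Total cumulative dose (mg) = sum of actual dose administered in all cycles while the patient is on study drug".
- Actual intensity divides that by a single weight: "Actual dose intensity (mg/kg/dose) = total cumulative dose (mg) / baseline weight (kg"). The result is then divided by treatment duration over cycle length, both in weeks.
- The relative measure follows: "Relative dose intensity (%) = actual dose intensity/planned dose intensity", expressed as a percentage. Planned dose intensity is not defined.

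SAP 4.2 and the opening of SAP 7 both fix baseline at or before the first dose, and neither updates it later.

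Protocol 6.7.1.1 (IMGC936 Dosage) sets the mg dose: "The calculated dose of IMGC936 will be administered based on the participant's body weight at Cycle 1, Day 1". It adds that "Body weight will be measured at screening and Day 1 of each cycle" and that a significant (at least 10%) "change in body weight from baseline should prompt recalculation of dose".

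Protocol 14.4 gives a different definition of dose intensity, as a percentage: "dose actually administered divided by total dose intended during the whole treatment period".

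**The concern.** The numerator and the divisor can rest on different weights. Until a recalculation, mg given equals assigned mg/kg times Cycle 1 Day 1 weight, and dividing by baseline weight returns the assigned mg/kg. After a recalculation, the mg follow the new weight while the SAP still divides by the old one. The result then mixes weight change with dose delivery.

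A participant who lost weight and missed nothing appears under-dosed. A participant who gained weight appears over-dosed, which could mask a missed or reduced dose. Nothing in the SAP adjusts for this. At stake is whether the exposure table for each dose level shows how much of the assigned treatment was delivered.

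**Working it through.** The documents state no dose-intensity figure, so there is none to reproduce. The check applies the SAP formula to a participant who receives every assigned dose in full and on time.

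**Inputs from the documents**
- Schedule A, one infusion per 21-day cycle (Protocol 6.1).
- 6 mg/kg, the dose that SAP 7 singles out for a combined summary.
- Recalculation when weight has changed by at least 10% from baseline (Protocol 6.7.1.1).
- Treatment duration = [(last − first infusion date) + cycle length] / 7 (SAP 7.1).

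**Assumptions, because the documents give no figures**
- Baseline weight is 70 kg and equals the Cycle 1 Day 1 weight.
- Six cycles are given. Weight changes once, before Cycle 3, and then stays constant.
- Dose rounding is ignored.
- Planned dose intensity is the assigned 6 mg/kg.

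**Formula**

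Duration = (5 × 21 + 21) / 7 = 18 weeks, and 18 / 3 = 6 cycle lengths.

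Actual dose intensity = total mg / 70 / 6. Relative dose intensity = actual / 6.

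| Weight from Cycle 3 | mg, Cycles 1–2 | mg, Cycles 3–6 | Total mg | Actual (mg/kg) | Relative |
|---|---|---|---|---|---|
| 70 kg, no change | 420 | 420 | 2520 | 6.00 | 100% |
| 66.5 kg, 5% loss (below trigger) | 420 | 420 | 2520 | 6.00 | 100% |
| 63 kg, 10% loss | 420 | 378 | 2352 | 5.60 | 93.3% |
| 60 kg, 14.3% loss | 420 | 360 | 2280 | 5.43 | 90.5% |
| 56 kg, 20% loss | 420 | 336 | 2184 | 5.20 | 86.7% |
| 77 kg, 10% gain | 420 | 462 | 2688 | 6.40 | 106.7% |

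The first two rows show that the formula is right when no recalculation occurs. The other four differ from 100% only because of the weight in the divisor.

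**General form.** With one recalculation at relative weight change *c*, and a fraction *f* of doses given after it, relative dose intensity = 1 + *f* × *c*. For a 10% loss, 1 − (4/6) × 0.10 = 0.933. For a 15% loss from Cycle 3 of 12, 1 − (10/12) × 0.15 = 0.875. The error cannot exceed the percentage weight change.

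**With the weight actually used.** For the fall to 60 kg, the sum of mg / dosing weight is 2 × (420/70) + 4 × (360/60) = 36. Then 36 / 6 = 6.0 mg/kg, or 100%. The same holds in every row.

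**Protocol 14.4 ratio, same participant.** If intended mg follow the recalculated weight, 2280 / 2280 = 100%. If intended mg stay at Cycle 1 Day 1 weight, 2280 / 2520 = 90.5%, the same error. Section 14.4 does not say which is meant.

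**The case against.** **The relative measure may be unaffected.** Planned dose intensity is undefined. If it were built from intended mg after recalculation over the same baseline weight, the weights would cancel and relative dose intensity would be 100%. That stands as a possibility. However, the SAP does not say so, and the unit it gives for actual intensity (mg/kg/dose) points to the assigned dose. Actual dose intensity in mg/kg is misstated under either reading.

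**Few participants may be affected, and the table may barely move.** The documents do not say how many reach a 10% change and have the dose recalculated. Suppose, purely as an assumption, that 5% to 20% of a dose level had a 10% loss from Cycle 3 of six. The dose-level mean would then fall by 0.05 × 6.7 = 0.3 to 0.20 × 6.7 = 1.3 points. This objection stands: the error can matter for an individual and still be small in a mean.

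**Stronger readings that the documents do not support.**
- A reader might infer that everyone who loses weight is reported as under-dosed. Below 10% the mg dose does not change and there is no error.
- A reader might infer that the choice of RP2D is affected, since 360/70 = 5.14 mg/kg per cycle (85.7% of 6) looks much like a one-level reduction to 5 mg/kg (83.3%). Protocol 4.4 names the proportion receiving planned doses and the percentages with reductions or discontinuations, not relative dose intensity. SAP 7 already singles out 6 mg/kg. SAP 7.1 also lists all administration records, so an individual case can be checked.
- A reader might infer that the measure will be set against response or ocular toxicity, or that the bias tracks tumor type. The SAP plans no such pairing, and neither document quantifies weight change by disease.
- A reader might take Protocol 14.4 as free of the problem. That depends on which weight defines the intended dose, and 14.4 is silent.

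**Conclusion.** The formula is wrong as written for participants whose dose has been recalculated under Protocol 6.7.1.1. Their actual dose intensity in mg/kg is understated after weight loss and overstated after weight gain, even with complete, on-time dosing. Relative dose intensity carries the same error if planned dose intensity means the assigned mg/kg.

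In the assumed six-cycle cases, the shortfall is about 7 to 13 points for losses of 10% to 20%, and the excess is about 7 points for a 10% gain. These sizes rest on the assumed 70 kg, recalculation from Cycle 3 and a single weight change. The number of participants affected is unknown.

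The consequence is confined to a descriptive exposure summary by dose level. ORR, DLT counts and decision rules are untouched. The point is modest but clear, and worth correcting before the tables are programmed.

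**What to change.** In SAP 7.1, replace total mg / baseline weight with the sum over infusions of (mg given / weight used to calculate that dose). Keep the rest of the formula, and define planned dose intensity as the assigned mg/kg. On Schedule B, which has two or three infusions per cycle, state the planned figure on the same basis as the actual one.

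Alternatively, adopt the Protocol 14.4 ratio of dose administered to dose intended, and state that intended mg use the weight in force at each infusion. Either route also resolves the difference between the two documents' definitions.

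The cost is a line or two of SAP text and a small programming change; the dosing rule is not touched. One practical limit is that SAP 4.1 takes data from the eCRF, while Protocol 6.8 only says that site staff keep dose-calculation records. If the dosing weight is not on the eCRF, derive it from the Day 1 weights and the 10% rule, and say so in the SAP.

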## 7.2. Adverse Events (AEs)

AEs will be documented on the AE eCRF and monitored continuously throughout the study from the time of informed consent until 30 days after the patient's last study drug or until the event has resolved, stabilized, or returned to baseline. AEs attributed to study procedures, including those events that occur prior to the first dose, should also be documented on the AE eCRF.

AE data are available to ImmunoGen from 2 sources, the eCRFs and the serious adverse event (SAE) forms. While reconciliation will be performed, the production of data summaries and listings will be based on the data collected on the eCRF.

Pre-treatment AEs are defined as AEs with an onset date prior to the first dose of study drug. TEAEs are defined as AEs with an onset date on or after the first dose of study drug, and within 30 days of the last dose of study drug or prior to the start of a new anti-cancer treatment, whichever occurs first. Medical history conditions that exist before the initiation of study drug but worsen in severity during the study will also be recorded on the AE eCRF as an AE and will be included as treatment-emergent in the summary tables and listings.

The adverse events will be coded using MedDRA, associating lower-level terms with PT and SOC by the primary hierarchy. The tables will display the counts and percentages of patients who reported at least 1 TEAE in each SOC represented in the AE data. Within each SOC, the tables will display the counts and percentages of patients reporting at least 1 TEAE as designated by the PT.

AEs are graded using Common Terminology Criteria for Adverse Events (CTCAE) Version 5.0. AE summaries may include summaries for all AEs and by the maximum CTCAE grade for the item being summarized (ie, SOC or PT). In these cases, the outputs will include a row for All Grades as well as rows for the 5 potential CTCAE grades, Grade 1 (Mild), Grade 2 (Moderate), Grade 3 (Severe), Grade 4 (Life threatening or disabling), or Grade 5 (Death). AEs missing a severity grade will not be included in the Grade 1-5 rows of the tables. An AE reported by a patient more than once will be represented in the most severe category.

Ocular AEs including blurred vision events and grouped keratopathy events will be analyzed for outcome, resolution, time to onset and time to resolution. Patients at 6mg/kg who administered different prophylactic eye drops will be further analyzed.

The criteria for eye drop subgroups are defined as follows.

Brimonidine + lubricating eye drop group: patient who started brimonidine prior to or on C1D1 reported in concomitant medicine or cycle 1 eye drop compliance form.

Steroid + lubricating eye drop group: patient who started steroid prior to or on C1D1 reported in concomitant medicine or cycle 1 eye drop compliance form.

Lubricating only eye drop group: all other patients at 6 mg/kg who are not included in above two groups.

The following AE summary tables will be produced:

- An overall summary: present the numbers (and percentages) of patients with any TEAEs, TEAEs ≥ Grade 3, study drug related AEs, AEs leading to permanent discontinuation of study drug, TEAEs leading to death, and any death during the study treatment or within 30 days of last dose.
- All TEAEs
- TEAEs with CTCAE severity Grade  $\geq 3$
- Study drug related TEAEs (ie, TEAEs with a drug relationship of possibly related, probably related, or definitely related; TEAEs with missing drug relationships will be also included).
- Study drug related TEAEs with CTCAE severity Grade  $\geq 3$
- Serious TEAEs
- Non-Serious TEAEs (ie, TEAEs excluding SAEs)

Confidential and Proprietary ImmunoGen, Inc.

- Study drug related SAEs
- TEAEs leading to discontinuation of study drug (ie, TEAEs with an action taken of study drug discontinued permanently)
- TEAEs leading to interruption of study drug (ie, TEAEs with an action taken of study drug with dose interrupted)
- Study drug related TEAEs leading to discontinuation of study drug
- Study drug related TEAEs leading to interruption of study drug
- TEAEs leading to death (ie, TEAEs with CTCAE Grade 5)
- Deaths on study treatment or within 30 days of the last dose. This table includes all deaths during study treatment or within 30 days of the last dose, regardless of cause of death.
- Ocular TEAE resolution (blurred vision and keratopathy)
- Time to onset of first ocular TEAE (blurred and keratopathy)

Time to resolution of ocular TEAE (blurred vision and keratopathy)The following listings will be produced:

- All pre-treatment AEs
- All TEAEs, sorted chronologically within patient. This listing includes SOC, PT, onset and end dates, and other relevant information.
- Serious TEAEs, sorted chronologically within patient
- TEAEs leading to discontinuation of study drug
- TEAEs leading to interruption of study drug
- Study drug related TEAEs
- Study drug related SAEs
- Dose-limiting toxicities (DLTs)
- TEAEs leading to death

The following PTs will be grouped for the analyses:

AEPT3	PTs		
Keratopathy	"Corneal cyst", "Corneal disorder", "Corneal epithelial microcysts",		
	"Keratitis", "Keratopathy", "Corneal opacity", "Corneal erosion",		
	"Corneal pigmentation", "Corneal deposits", "Keratitis interstitial",		
	"Punctate keratitis", "Corneal epithelium defect", "Corneal epithelial		
	microcysts", "Limbal stem cell deficiency"		
Blurred vision event	"Vision blurred", "Visual impairment", "Vitreous floaters", "Visual		
	acuity reduced", "Diplopia", "Presbyopia", "Accommodation disorder",		
	"Refraction disorder", "Hypermetropia"		
Dry eye	"Lacrimation decreased", "Dry eye"		

AEPT3	PTs
Cataract	"Cataract", "Cataract nuclear", "Cataract cortical"
Eye pain	"Eye pain"
Ocular discomfort "Eye pruritus", "Eye irritation", "Ocular discomfort", "Foresensation in eyes"	
Peripheral neuropathy "Neuropathy peripheral", "Peripheral sensory neuropathy", "Peripheral sensory neuropathy", "Peripheral sensorimotor neuropathy", "Peripheral sensorimotor neuropathy"	
Pneumonitis "Pneumonitis", "Interstitial lung disease", "Pulmonary fibrosis", "Organizing pneumonia", "Organising pneumonia"	
Abdominal pain "Abdominal pain", "Abdominal pain upper", "Abdominal pain lo "Abdominal discomfort"	
Fatigue	"Fatigue", "Asthenia"
Dyspnea	"Dyspnea", "Exertional dyspnea"
Hypertension	"Hypertension", "Increased blood pressure", "High blood pressure"
Hypokalaemia	"Hypokalaemia", "Blood potassium decreased"
Hyponatraemia	"Hyponatraemia", "Blood sodium decreased"
Hypomagnesaemia	"Hypomagnesaemia", "Blood magnesium decreased"
Thrombocytopenia	"Thrombocytopenia", "Platelet count decreased"

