3.2.3. Exploratory Objectives and Endpoints

- To explore potential biomarkers of clinical and/or immunologic response to IMGC936 in blood and tumor tissue
 - o Change in soluble ADAM9 levels over time
 - Correlation of potential biomarkers (FcγR genotype, soluble ADAM9, cell-free tumor DNA) and response
- To explore the relationship between baseline ADAM9 expression and antitumor activity
 - Correlation of ADAM9 expression and response
- To explore ocular primary prophylaxis regimens
 - o Frequency and severity of ocular events

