4.1.3. Eye Drop Sub-Study

4.1.3.1. Sub-Study Schema

4.1.3.2. Sub-Study Design

Up to 60 participants from Cohorts A to G may voluntarily consent to join a sub-study to evaluate the effect of different prophylactic eye drops, beyond standard lubricating eye drops. Consenting participants will be assigned to cohorts of 10 to 20 participants who will receive additional eye drops as primary prophylaxis to mitigate ocular symptoms and signs. Participants in this sub-study will be monitored for the frequency and severity of ocular events and will have an ocular examination after 2 cycles of therapy regardless of whether they have ocular symptoms and signs, as required of all participants in this trial. Major differences in ocular AEs (eg, 50% reduction in participants with ≥ Grade 2 keratopathy, or 50% reduction in ocular AEs leading to dose reduction/discontinuation) will be used to determine whether different eye drop regimens provide benefit in comparison to others and to participants on trial that only receive prophylactic lubricating drops. Knowledge gained from this sub-study may be applied to the remainder of the study participants. Details of the eye drop options are described in Section 7.2.1.

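### The SAP commits to no table by eye-drop group of the ocular measures the protocol names for judging prophylaxis, and to no dose-reduction output at all

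*SAP*

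**What the plan says.** **Protocol.** Section 3.2.3 gives the endpoint for the prophylaxis objective as "Frequency and severity of ocular events". Section 4.1.3.2 describes the sub-study: "Up to 60 participants from Cohorts A to G may voluntarily consent to join a sub-study", in cohorts of 10 to 20. Major differences in ocular events "will be used to determine whether different eye drop regimens provide benefit in comparison to others", and also in comparison with participants on lubricating drops only. Two examples of a major difference follow: a "50% reduction in participants with ≥ Grade 2 keratopathy", or a "50% reduction in ocular AEs leading to dose reduction/discontinuation". What is learned may be applied to the remaining participants. Section 14.5.1 includes ocular AEs in its list of summary tables with number and percent of participants.

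**SAP.** The SAP governs the analysis (Protocol 14, SAP 1.1). Section 7.2 states: "Ocular AEs including blurred vision events and grouped keratopathy events will be analyzed for outcome, resolution, time to onset and time to resolution". Its itemised ocular tables are resolution, time to resolution and "Time to onset of first ocular TEAE (blurred and keratopathy"). It defines three groups at 6 mg/kg (brimonidine plus lubricating, steroid plus lubricating, lubricating only) and says that these patients will have further analysis, without naming a measure. Default safety columns in SAP 7 are dose level, combined 6 mg/kg and overall.

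**The concern.** A prophylaxis question asks how many participants develop the event and how bad it is. That is what the protocol endpoint measures. The ocular tables that the SAP itemises answer different questions: when the first event began, and whether and how fast it cleared. Resolution is observed only in participants who already have an event, so by itself it cannot show prevention.

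Dose reduction matters beyond the sub-study. Protocol 7.2 treats ocular toxicity as limited if, for example, it does not lead to dose reductions or discontinuations in more than 10% of participants. Protocol 4.4 asks for the percentage of participants needing dose reductions at cohort review. Table 7 makes resumption at a lower dose level one outcome of Grade 2 and Grade 3 ocular events. If the SAP's table list is followed as written, those reductions are not counted anywhere.

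The study is open-label. If the by-regimen measure is left open, it can be chosen after the data have been seen, and the result may shape what later participants receive.

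**Working it through.** The documents give no sample-size calculation, error rate or base rate for the sub-study, so there is no figure to reproduce. The check sets each part of the protocol's endpoint and benchmarks against the outputs named in SAP 7, 7.2 and 7.11.

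| Protocol element | Named in the SAP? | Committed by eye-drop group? |
|---|---|---|
| Participants with Grade 2 or higher keratopathy | No such table. Keratopathy preferred terms are grouped, and AE summaries *may* include rows for Grades 1 to 5 by maximum grade, so Grades 2 to 5 could be summed if that optional table is made. The only named severity cut is Grade 3 or higher | No |
| Ocular AEs leading to discontinuation | Partly. Discontinuation TEAEs are tabulated by system organ class and preferred term under the default dose-level columns, with no ocular total specified | No |
| Ocular AEs leading to dose reduction | No table or listing. The action-taken outputs are discontinuation and interruption | No |
| All ocular AEs (Protocol 14.5.1) | Not itemised in 7.2. SAP 7.11 refers to ocular TEAE tables without defining any beyond those in 7.2 | No |

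Count over the three benchmark components: committed by regimen, 0 of 3; optional or partly available at dose level, 2 of 3; in no named output, 1 of 3 (dose reduction).

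**Does the interruption table stand in for dose reduction?** No. Under Table 7 a Grade 2 ocular event leads to a hold. Dosing may then resume at the same level if the event resolves to Grade 1 or less within 14 days, or one level lower if that takes more than 14 and up to 28 days. Both paths count as an interruption, so the interruption count cannot separate them.

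**Are the data there?** Yes. Protocol 12.2.1 requires each AE record to hold severity and the action taken with study drug.

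**How much could the added tables show?** The base rate is not given, so the rates here are assumptions. The exact (Clopper-Pearson) 95% interval for x of n is Beta(0.025; x, n−x+1) to Beta(0.975; x+1, n−x). For a halving:

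- n = 20, 60% to 30%: 12/20 gives 36.1% to 80.9%; 6/20 gives 11.9% to 54.3%.
- n = 20, 40% to 20%: 8/20 gives 19.1% to 63.9%; 4/20 gives 5.7% to 43.7%.
- n = 20, 20% to 10%: 4/20 gives 5.7% to 43.7%; 2/20 gives 1.2% to 31.7%.
- n = 10, 40% to 20%: 4/10 gives 12.2% to 73.8%; 2/10 gives 2.5% to 55.6%.

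The two intervals overlap widely in each case. The tables would describe the groups; they would not establish a 50% reduction.

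**The case against.** The strongest reply is that the gap is one of detail. The objective is exploratory, the 50% figures are examples, and the SAP already groups keratopathy terms, allows maximum-grade rows, tabulates discontinuations and defines the eye-drop groups. The promised further analysis could well be a split by group. Protocol 14.5.1 lists no dose-reduction table either, so the SAP did not drop one promised there. Time to resolution also bears on dose reduction, because Table 7 ties the resumption level after a Grade 2 event to how long resolution took.

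Most of this is correct, and it limits the point. A reader might infer that the protocol fixes a binding benefit criterion that the planned outputs cannot deliver. The documents do not support that: the benchmarks are illustrative, and two of the three components can be partly derived. A reader might also infer that time to onset merely mirrors the examination calendar (end of Cycles 2, 5 and 8; Weeks 6, 15 and 24 on 21-day cycles). That applies only to asymptomatic findings, since ocular symptoms or signs of any grade trigger a complete examination (Protocol 7.2), and the asymptomatic share is not given.

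What survives is that possible outputs are not commitments. The endpoint itself, frequency and severity, is not offered as an example, and the SAP's itemised ocular tables measure something else.

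**Conclusion.** The point holds in a limited form. The SAP commits to none of the three benchmark components by eye-drop group, names no dose-reduction output, and does not itemise the ocular AE table of Protocol 14.5.1. Grade 2 or higher keratopathy and discontinuations are recoverable in part, but not by regimen under any named table.

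The gap affects an exploratory objective and the dose-reduction reporting. It does not touch the ORR objective. How far it would change a decision on eye drops cannot be sized, because the documents give no ocular event rates and do not say that the decision waits for SAP tables. The conclusion rests on reading SAP 7.2's list as the set of tables to be produced, and on further analysis meaning no specified output.

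The populations also differ. The sub-study is up to 60 consenting participants from Cohorts A to G, whereas the SAP groups take in all patients at 6 mg/kg, classified from medication or compliance forms. SAP group sizes may therefore differ from 10 to 20.

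**What to change.** In SAP 7.2, add the following by eye-drop group, each with counts, denominators and exact 95% confidence intervals:

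1. Participants with Grade 2 or higher keratopathy, using the grouped preferred terms.
2. Participants with an ocular TEAE leading to dose reduction, and participants with one leading to discontinuation, shown separately.
3. All ocular TEAEs by maximum grade.

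Also add an overall table and listing of TEAEs leading to dose reduction. State that the by-regimen comparison is descriptive, because the sub-study cohorts are small and no randomisation is described. Keep the onset and resolution tables as supportive.

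Before programming, make the groups mutually exclusive and complete. As written, a patient starting both brimonidine and steroid meets two definitions, and a patient using cyclosporine drops (an option in Protocol 7.2.1) without either of those falls into lubricating only.

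The cost is SAP text and a few extra tables from grade and action-taken data already collected. No new data and no change to any clinical rule are needed.
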